Study Population:	Subjects with active, moderate to severe Crohn's Disease (CD). The following inclusion criteria apply: • Males and females 18 to 75 years of age. • Signed fully informed consent provided as per this protocol. • Diagnosis of Crohn's Disease confirmed by endoscopy or radiography and/or histology at least 6 months prior to randomization into the study. • CD involving the ileum and/or colon • Moderately to severely active CD (Crohn's Disease Activity Index (CDAI) score of ≥ 220 and ≤450) at baseline. • Current treatment with at least one of the following therapies: • Oral 5-aminosalicylic acid (5-ASA) compounds • Dose must be stable for at least 4 weeks before baseline • Corticosteroid therapy • Dose must be stable for at least 2 weeks before baseline • Azathioprine or 6-mercaptopurine (6-MP) or methotrexate • Dose must be stable for at least 8 weeks before baseline • Infliximab or adalimumab • Dose must be stable for at least 14 weeks before baseline • White blood cell count ≥ 3.5x10° at screening. • Active Crohn's disease, defined by at least one of the following: C-reactive protein > Upper Limit of Normal (ULN) at screening, OR radiographic (MRE or CTE) or endoscopic confirmation of the presence of active CD within 5 weeks of screening visit. • Subject agrees to use the following effective contraceptive methods only • diaphragm, cervical cap, contraceptive sponge or condom with spermicidal foam/gel/cream/suppository • IUD/IUS • progestogen injection (Depo-Provera®) throughout the study and for at least 6 weeks after last study drug administration, unless subject or partner of subject is post-menopausal or otherwise incapable of becoming pregnant by reason of surgery or tubal ligation, or has had a vasectomy. In regions where local regulatory						
	contraceptive requirements differ, the ICF will reflect local policies. The following key exclusion criteria apply: Crohn's disease involvement isolated to the mouth, upper gastrointestinal tract, or anus.						

	History of total colectomy with ileorectal anastomosis or a proctocolectomy.				
	 Presence of active fistulizing Crohn's Disease or healed fistula within 2 m prior to screening. 				
	Subject has postoperative stoma, ostomy, or ileoanal pouch.				
	Subject has short bowel syndrome.				
	Subject is scheduled for surgical bowel resection.				
	 Subject has known symptomatic obstructive strictures or bowel perforation in the 6 months prior to screening. 				

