2.2.3.3 Endoscopic Change Variables

- Change from baseline to week 26 in Crohn's Disease Endoscopic Index of Severity (CDEIS) and Simple Endoscopic Score for Crohn's Disease (SES-CD). The CDEIS and SES-CD are endoscopic scoring systems for the assessment of CD.
- Correlations between the change from baseline to week 26 in CDEIS and SES-CD and the change from baseline to week 26 in CDAI.
- Proportion of subjects in remission by visit time post-baseline based on CDEIS and SES-CD measurements. Remission is defined as 0-3 score based on CDEIS measurement and defined as 0-2 score based on SES-CD measurement.
- Proportion responders based on CDEIS and SEC-CD at week 26. Responders based on CDEIS and SES-CD scores are defined and classified into two categories as 50% reduction from baseline score; and 25% reduction from baseline score to week 26.

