Logistic regression modeling will be implemented as additional exploratory analysis to assess the modifying effect of prognostic baseline characteristics identified prospectively as clinically important baseline factors/variables on the remission outcome in both treatment groups at week 26. This will model a categorical response variable Remission (< 150 CDAI score) at week 26 (yes/no) as a function of treatment, stratification anti-TNF agents (yes/no) use, and treatment-by-baseline clinical factor interaction. The aim is to assess consistence/inconsistence of the treatment differences across each of the pre-defined clinically important baseline characteristics (one-variable-at-a-time). Each prognostic factor will be fitted separately (one-variable-at-a-time) in the model and output results including 95% confidence intervals presented in forest plots showing consistence/inconsistence by treatment group. The following baseline factors are considered prospectively to be potentially clinically important:

- Baseline serum inflammation marker: C-reactive protein (Normal/High)
- Baseline stool inflammation marker: Fecal calprotectin (Normal/High)
- Baseline CDEIS score (0-3; >3 score)
- Baseline SES-CD score (0-2; >2 score)
- Baseline IBDQ Score
- Duration of CD
- Prior surgical treatment for CD (yes/no)
- MAP-Test PCR Blood assay (Positive/Negative) Baseline
- MAP-Test Blood culture (Positive/Negative) Baseline
- Gender (male/female)
- Age at first Diagnosis of CD
- Smoking (yes/no)
- Alcohol consumption (yes/no)
- Use of Immunomodulators (yes/no)
- Use of steroids (yes/no)

The continuous variables may be categorized into different classification categories depending on the number of observations and final decisions on categories for each variable will be determined at the time of analysis.

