6.3.3.8 Serum Marker of Inflammation: C-reactive Protein (CRP)

The CRP is used as marker of inflammation. The C-reactive Protein (CRP) level data collected at different visits will be used to assess inflammation at baseline and at different visits post-baseline. Summary descriptive statistics for the actual observed and change from baseline will include mean, standard deviation, median and range for each treatment by visit. The change from baseline CRP comparing the two treatment groups will be analyzed using an analysis of covariance (ANCOVA) model with treatment group, stratification variable anti-TNF agents use (yes/no) as classification factors, and baseline CRP as a covariate. The treatment parameter estimates from the analysis model including means, 95% confidence intervals and associated 2-sided p-values will be presented including bar graphs.

In addition, the CRP level will be classified into two categories: “Normal (≤ 0.999 mg/dL)” and “High (> 10 mg/dL)”. Summary results will show number of patients and proportion (%) with “Normal level” and with “High Level” by treatment group at baseline and at different visit time-points with data collected post-baseline. The same statistical method and modeling as used for the primary endpoint will be used for this analysis. The proportion of subjects “Normal” at baseline and at each visit with data post-baseline will be compared between the two treatments using Cochran-Mantel-Haenszel (CMH) chi-square test controlling for the stratification variable anti-TNF agents use (yes/no).

Supplementary shift tables will be presented showing proportion of subjects at baseline that were in each category and shifted from one category to another or remained in the same category at the different post-baseline visits.

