6.3.3.9 Stool Marker of Inflammation: Fecal calprotectin

The fecal calprotectin is used as marker of inflammation. The level of fecal calprotectin data collected at different visits will be used to assess inflammation at baseline and at different visits post-baseline. Summary descriptive statistics for the actual observed and change from baseline will include mean, standard deviation, median and range for each treatment by visit. The change from baseline Fecal calprotectin comparing the two treatment groups will be analyzed using an analysis of covariance (ANCOVA) model with treatment group, stratification variable anti-TNF agents use (yes/no) as classification factors, and baseline Fecal calprotectin as a covariate. The treatment parameter estimates from the analysis model including means, 95% confidence intervals and associated 2-sided p-values will be presented including bar graphs.

In addition, fecal calprotectin will be classified into two categories: “Normal (≤ 162.9 mcg/g)” and “High (> 162.9 mcg/g)”. Summary results will show number of patients and proportion (%) with “Normal level” and with “High Level” by treatment group at baseline and at different visit time-points with data collected post-baseline. The same statistical method and modeling as used for the primary endpoint will be used for this analysis. The proportion of subjects “Normal” at baseline and each visit with data post-baseline will be compared between the two treatments using Cochran-Mantel-Haenszel (CMH) chi-square test controlling for the stratification variable anti-TNF agents use (yes/no).

Supplementary shift tables will be presented showing proportion of subjects at baseline that were in each category and shifted from one category to another or remained in the same category at the different post-baseline visits.

6.3.3.10 Endoscopic Assessment Based on CDEIS and SES-CD at Week 26

The Crohn's Disease Endoscopic Index of Severity (CDEIS) is a validated quantitative measure of disease severity upon endoscopy. The score ranges from 0-44 based upon the extent and severity of inflammation and ulcers seen during endoscopy of the colon. A response is a drop in score from baseline.

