The Simple Endoscopic Score for Crohn's Disease (SES-CD) is a validated quantitative measure of disease severity upon endoscopy that is based on four endoscopic variables (presence and size of ulcers, proportion of surface covered by ulcers, proportion of surface affected by disease, and presence and severity of stenosis). Each variable is assessed in each of the five ileocolic segments: Rectum, sigmoid and left colon, transverse colon, right colon, and ileum. Each of the four SES-CD variables is scored from 0 to 3, with the sum of the scores for each variable ranging from 0 to 15, except for the presence and extent of stenosis, which ranges from 0 to 11 (Total SES-CD score range 0-56).

The CDEIS and SES-CD mean scores at baseline and week 26, and change from baseline scores to week 26 will be summarized by treatment group for subjects who consent to undergo colonoscopy. The change from baseline CDEIS and SES-CD scores comparing the two treatment groups based on each of the two scoring systems will be analyzed using analysis of covariance (ANCOVA) models with treatment group, stratification variable anti-TNF agents use (yes/no) as classification factors, and baseline CDEIS score or SES-CD as covariate. The treatment parameter estimates from the analysis models including means, 95% confidence intervals and associated 2-sided p-values will be presented.

In addition, the CDEIS and SES-CD scores will be classified into two categories: "Remission (CDEIS 0-3 score; SES-CD 0-2 score)" and "No Remission (CDEIS > 3; SES-CD > 2 score)". Summary results will show number of patients and proportion (%) in "Remission" based on CDEIS and also based on SES-CD by treatment group at baseline and at different visit time-points with data collected post-baseline. The same statistical method and modeling as used for the primary endpoint will be used for this analysis.

The proportion of subjects at baseline and each visit in "Remission post-baseline will be compared between the two treatments using Cochran-Mantel-Haenszel (CMH) chi-square test controlling for the stratification variable anti-TNF agents use (yes/no). The same statistical summary will be repeated comparing the two treatment groups on proportion of responders based on CDEIS and SES-CD scores defined as 50% reduction from baseline score and 25% reduction from baseline score to week 26.

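### The Normal/High tests for CRP and fecal calprotectin and the endoscopic remission test leave out baseline category, so subjects already normal at entry who stay normal count as successes

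*SAP*

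**What the plan says.** **The tests.** For CRP (SAP 6.3.3.8) the proportion Normal is compared "at baseline and at each visit with data post-baseline will be compared between the two treatments using Cochran-Mantel-Haenszel (CMH) chi-square test controlling for" anti-TNF use. For fecal calprotectin (6.3.3.9) it is compared "at baseline and each visit with data post-baseline will be compared between the two treatments", again by CMH. For endoscopic remission (6.3.3.10) the same clause recurs: the proportions "will be compared between the two treatments using Cochran-Mantel-Haenszel (CMH) chi-square test controlling for the stratification variable anti-TNF agents use (yes/no"). Anti-TNF use is the only factor in all three sections, and none of them limits the test to subjects abnormal at baseline.

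**The endoscopic definition.** SAP 2.2.3.3 sets an absolute threshold with no baseline condition: "Remission is defined as 0-3 score based on CDEIS measurement and defined as 0-2 score based on SES-CD measurement".

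**Who can enter.** The protocol synopsis accepts either of two routes to active disease: "C-reactive protein > Upper Limit of Normal (ULN) at screening, OR radiographic (MRE or CTE) or endoscopic confirmation of the presence of active CD". A raised CRP is therefore not required. The criteria in the synopsis set no calprotectin threshold and no minimum endoscopic score. SAP 6.3.1 plans for such subjects: its list of baseline factors has Normal/High for both markers, SES-CD split at 2, and "Baseline CDEIS score (0-3; >3 score").

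**What else the sections contain.** Each one also specifies an ANCOVA of change with the baseline value as covariate, and shift tables by baseline category. SAP 6.3.3 classes all these endpoints as supportive, without multiplicity adjustment.

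**The concern.** The supportive objective is the effect of RHB-104 on inflammation and on the mucosa. The question a reader brings to a Normal/High table is whether more inflamed subjects became normal on active treatment. The planned test answers a different one: whether more subjects were normal at the visit, however they started.

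A subject who enters normal and stays normal is a success in either arm and says little about treatment. The more such subjects there are, the smaller the difference between arms. A chance imbalance in the baseline-normal share also feeds into the result. Baseline category is already collected and is likely to be the strongest predictor of later category, so leaving it out gives up precision that costs nothing to keep.

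The same sentences also test the arms against each other at baseline. After randomisation any difference there is chance, so that p-value carries no information.

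**Working it through.** **1. The plan's own figures.** The SAP gives no power for these tests, only for the primary endpoint (SAP 6.1.9). With n per arm, rates p0 and p1, and p̄ their mean:

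power = Φ{ [ (p1−p0)√n − 1.96√(2p̄(1−p̄)) ] / √(p0(1−p0)+p1(1−p1)) }

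For 21% vs 36%:
- n = 162: (0.15×12.728 − 1.96×0.6384)/0.6295 = 1.045, so 85%. This agrees with the stated figure of at least 80%.
- n = 205: 1.424, so 92%. This agrees with the stated 90%; a continuity-corrected calculation gives a total of 404 to 406 against the stated 410.

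The formula can therefore be carried to the marker tests.

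**2. Assumptions, none of them in the documents except n.**
- n = 162 per arm (SAP 6.1.9), every randomised subject counted; two-sided 0.05.
- q = share normal at baseline, varied.
- 85% of baseline-normal subjects stay normal in both arms.
- 25% (placebo) vs 40% (RHB-104) of baseline-High subjects normalise.

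**3. Dilution.** The proportion Normal at the visit is 0.85q + (1−q)×0.25 on placebo and 0.85q + (1−q)×0.40 on RHB-104. The difference is 0.15(1−q).

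**4. Worked case, q = 30%.**
- As planned: p0 = 0.255 + 0.175 = 0.430; p1 = 0.255 + 0.280 = 0.535; difference 10.5 points. (0.105×12.728 − 1.96×0.7067)/0.7028 = −0.07, so 47% (48% by simulation).
- Baseline-High only: n = 162×0.7 = 113.4. (0.15×10.649 − 1.96×0.6624)/0.6538 = 0.457, so 68%.

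**5. Simulated power.** The baseline split is drawn at random in each arm.

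| Normal at baseline | Difference as planned (points) | As planned | Baseline added as CMH stratum | Baseline-High only |
|---|---|---|---|---|
| 10% | 13.5 | 71% | 76% | 78% |
| 20% | 12.0 | 59% | 68% | 74% |
| 30% | 10.5 | 48% | 58% | 68% |
| 50% | 7.5 | 27% | 37% | 53% |

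**6. Other rates.** With 21% vs 36% normalising and 90% staying normal, the same three columns are 73/79/81% at 10%, 60/72/77% at 20%, 47/63/71% at 30% and 28/42/56% at 50%. The pattern does not depend on one choice of rates.

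**7. Chance imbalance.** The SD of the between-arm difference in baseline-normal share is √(2q(1−q)/162), which is 5.1 points at q = 30%. Since 85% − 25% = 60% of that carries into the placebo-type outcome, about 3.1 points reach the unadjusted result. The nominal error rate already allows for this. In simulation under no effect (both arms normalising at 25%), the planned test rejects in about 5% of trials.

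**8. Endoscopy.** SAP 6.3.3.10 covers only subjects who consent to colonoscopy and gives no number, so the table does not apply there. The direction is the same.

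**9. CRP categories.** SAP 6.3.3.8 sets Normal at 0.999 mg/dL or below and High above 10 mg/dL. Values between the two belong to neither category, so neither the planned test nor a baseline stratum can be built as written.

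**The case against.** The strongest reply is that baseline is already handled where it matters. In each section the first between-arm analysis is an ANCOVA with the baseline value as covariate; the categorical test is an addition; and shift tables show transitions. The endpoints are supportive, and type I error is intact. All of this stands, and it limits the weight of the point. It does not remove it: the ANCOVA tests mean change, not normalisation, and the shift tables carry no test. Sections 6.3.3.8 to 6.3.3.10 do refer to the primary endpoint's modeling, but the logistic models in SAP 6.3.1 are specified for CDAI remission, and the table list in SAP 8.1 has no such model for the markers or the endoscopic scores.

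Three stronger readings are tempting and are not supported.

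- *A reader might infer that most of the power is lost.* The documents give no baseline-normal share. Planned power falls to about half that of the baseline-High analysis only when the share is near 50%. Part of the fall from about 83% (nobody normal at entry) reflects fewer informative subjects, which no analysis recovers.
- *A reader might infer that the endoscopic response tests share the fault.* They do not. SAP 2.2.3.3 and 6.3.3.10 define response as a 25% or 50% reduction from the subject's own baseline, so an unchanged subject with a low score is a non-responder. The gap there is narrower: a baseline score of 0 has no defined percentage reduction.
- *A reader might infer that the tests are invalid because of baseline imbalance.* Randomisation protects the error rate; the loss is in precision.

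Restricting to subjects abnormal at baseline also has a price. It shrinks the denominator, most of all in the optional endoscopy subset, and gives different populations for CDEIS and SES-CD.

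**Conclusion.** The point holds for three tests: CRP Normal, calprotectin Normal and endoscopic remission. They control only for anti-TNF use, so subjects already normal or in endoscopic remission who remain so are counted as successes and the difference is diluted. No planned test addresses normalisation given baseline status.

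Under the stated assumptions, adding a baseline stratum recovers about 5 points of power at a 10% baseline-normal share, 9 at 20%, and 10 at 30% and 50%. Analysing baseline-High subjects alone recovers about 7, 15, 20 and 26 points. The share and the rates are assumptions, and no figure is claimed for endoscopy. The primary and key secondary conclusions are untouched. This is an inexpensive improvement that should be made, not a threat to validity.

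**What to change.** 1. Reconcile the CRP cut-offs in SAP 6.3.3.8 first, so that every value falls in one category.
2. In 6.3.3.8 to 6.3.3.10, add baseline category (Normal/High; remission/no remission) as a second CMH stratification factor for the post-baseline tests, and say how subjects without a baseline value are handled.
3. Report, as a supplementary result with its denominator, normalisation among subjects High at baseline and endoscopic remission among subjects with baseline CDEIS above 3 (or SES-CD above 2).
4. Keep the baseline proportions as description and drop the between-arm test at baseline.
5. State a rule for the 25% and 50% endoscopic response when the baseline score is 0.

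The cost is SAP wording, table footnotes and one supplementary row per table; no new data are needed. The downside is the smaller denominator in item 3 and possibly sparse strata in the endoscopy subset. SAP 6.8 allows such changes before unblinding; made later, the restricted analysis would be post hoc.

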6.3.3.9 Stool Marker of Inflammation: Fecal calprotectin

The fecal calprotectin is used as marker of inflammation. The level of fecal calprotectin data collected at different visits will be used to assess inflammation at baseline and at different visits post-baseline. Summary descriptive statistics for the actual observed and change from baseline will include mean, standard deviation, median and range for each treatment by visit. The change from baseline Fecal calprotectin comparing the two treatment groups will be analyzed using an analysis of covariance (ANCOVA) model with treatment group, stratification variable anti-TNF agents use (yes/no) as classification factors, and baseline Fecal calprotectin as a covariate. The treatment parameter estimates from the analysis model including means, 95% confidence intervals and associated 2-sided p-values will be presented including bar graphs.

In addition, fecal calprotectin will be classified into two categories: “Normal (≤ 162.9 mcg/g)” and “High (> 162.9 mcg/g)”. Summary results will show number of patients and proportion (%) with “Normal level” and with “High Level” by treatment group at baseline and at different visit time-points with data collected post-baseline. The same statistical method and modeling as used for the primary endpoint will be used for this analysis. The proportion of subjects “Normal” at baseline and each visit with data post-baseline will be compared between the two treatments using Cochran-Mantel-Haenszel (CMH) chi-square test controlling for the stratification variable anti-TNF agents use (yes/no).

Supplementary shift tables will be presented showing proportion of subjects at baseline that were in each category and shifted from one category to another or remained in the same category at the different post-baseline visits.

6.3.3.10 Endoscopic Assessment Based on CDEIS and SES-CD at Week 26

The Crohn's Disease Endoscopic Index of Severity (CDEIS) is a validated quantitative measure of disease severity upon endoscopy. The score ranges from 0-44 based upon the extent and severity of inflammation and ulcers seen during endoscopy of the colon. A response is a drop in score from baseline.

The Simple Endoscopic Score for Crohn's Disease (SES-CD) is a validated quantitative measure of disease severity upon endoscopy that is based on four endoscopic variables (presence and size of ulcers, proportion of surface covered by ulcers, proportion of surface affected by disease, and presence and severity of stenosis). Each variable is assessed in each of the five ileocolic segments: Rectum, sigmoid and left colon, transverse colon, right colon, and ileum. Each of the four SES-CD variables is scored from 0 to 3, with the sum of the scores for each variable ranging from 0 to 15, except for the presence and extent of stenosis, which ranges from 0 to 11 (Total SES-CD score range 0-56).

The CDEIS and SES-CD mean scores at baseline and week 26, and change from baseline scores to week 26 will be summarized by treatment group for subjects who consent to undergo colonoscopy. The change from baseline CDEIS and SES-CD scores comparing the two treatment groups based on each of the two scoring systems will be analyzed using analysis of covariance (ANCOVA) models with treatment group, stratification variable anti-TNF agents use (yes/no) as classification factors, and baseline CDEIS score or SES-CD as covariate. The treatment parameter estimates from the analysis models including means, 95% confidence intervals and associated 2-sided p-values will be presented.

In addition, the CDEIS and SES-CD scores will be classified into two categories: "Remission (CDEIS 0-3 score; SES-CD 0-2 score)" and "No Remission (CDEIS > 3; SES-CD > 2 score)". Summary results will show number of patients and proportion (%) in "Remission" based on CDEIS and also based on SES-CD by treatment group at baseline and at different visit time-points with data collected post-baseline. The same statistical method and modeling as used for the primary endpoint will be used for this analysis.

The proportion of subjects at baseline and each visit in "Remission post-baseline will be compared between the two treatments using Cochran-Mantel-Haenszel (CMH) chi-square test controlling for the stratification variable anti-TNF agents use (yes/no). The same statistical summary will be repeated comparing the two treatment groups on proportion of responders based on CDEIS and SES-CD scores defined as 50% reduction from baseline score and 25% reduction from baseline score to week 26.

Supplementary shift tables will be presented showing proportion of subjects at baseline that were in "No Remission" category and shifted to "Remission" category or vice versa or remained in the same category at the different post-baseline visits.

The following highlights the efficacy summaries in form of tables and/or figures that will be displayed by treatment group for both the CDEIS and SES-CD outcomes assessments:

- Endoscopic Remission based CDEIS and SES-CD week 26

- Shift Tables from “No Remission” to Remission and vice versa
- Endoscopic Response: 50% reduction in CDEIS and SES-CD scores from baseline
- Endoscopic Response: 25% reduction in CDEIS and SES-CD scores from baseline

Additional supportive analysis will be implemented to estimate the correlations between the change from baseline to week 26 in the SES-CD total score, CDEIS total score, and the change from baseline to week 26 in the CDAI total score. The results will be presented in graphs including Pearson and Spearman correlation coefficients estimates. Scatter plots of the change in SES-CD total score and CDEIS total score versus the change in CDAI total score will be presented.

Listing of all subjects indicating CDEIS and SES-CD scores by visit by treatment group will be presented.

